### 5.5.1 ARMS A and D and Arms C and F: Patients Receiving Ipilimumab

#### 5.5.1.1 **Dose and Schedule Modifications for Arms A and D (Ipilimumab 10 mg/kg)**

There will be no dose reductions for ipilimumab. The dose of ipilimumab will either be given or delayed/discontinued. Patients may develop study drug-related toxicities that may require skipping doses or dose discontinuation. Some of these adverse events may be consistent with potentially drug-related immune-mediated phenomena; termed IRAEs ([Appendix XIII-Appendix XVII](#)). Details of how to dose study medication in the presence of adverse drug reactions that may or may not be IRAEs are addressed below.

Patients will delay or discontinue treatment with ipilimumab if they experience at least one adverse event, specified below, considered by the investigator to be **certainly**, **probably**, or **possibly** related to ipilimumab treatment unless otherwise specified. The following criteria will be used to determine dosing delay, restarting doses, or discontinuing ipilimumab. For an adverse event, review the following criteria in a stepwise manner: First, assess the dose delay criteria and decide whether a scheduled dose should be delayed. Second, determine whether the permanent discontinuation criteria apply to the adverse event in question as well.

**NOTE:** Due to the possible effect of treatment with ipilimumab on the immunologic response to infectious disease vaccines, patients must not have had any infectious disease vaccination (e.g., standard influenza, H1N1 influenza, pneumococcal, meningococcal, tetanus toxoid) 4 weeks before or after any dose of ipilimumab.

5.5.1.1.1 **Criteria to delay/skip one dose of ipilimumab on Arms A or D (ipilimumab 10 mg/kg)**

Delay ipilimumab dosing for any of the following certainly, probably, or possibly treatment related adverse events, unless otherwise specified:

- Grade  $\geq$  1 diarrhea and/or colitis **regardless of attribution**. Grade  $\geq$  2 diarrhea and/or colitis, certainly, probably, or possibly related to ipilimumab, requires permanent discontinuation (Section [5.5.1.1.3](#)).
- Any other  $\geq$  Grade 2 non-skin related adverse event (including IRAEs) except for laboratory abnormalities.

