- Grade  $\geq$  2 laboratory abnormalities that are secondary to an immune-related adverse event or autoimmune phenomenon (e.g., Grade  $\geq$  2 TSH associated with a CTCAE v.4 grade 2 thyroid dysfunction induced by ipilimumab, anemia, neutropenia, amylase, lipase, CPK, hyperglycemia, or elevated LFTs) should also lead to an ipilimumab dosing delay/skipping.
- Any other  $\geq$  Grade 3 laboratory abnormality.
- Any  $\geq$  Grade 3 skin-related adverse event (including IRAEs) **regardless of attribution**.

5.5.1.1.2 **Criteria to resume ipilimumab treatment on Arms A or D (ipilimumab 10mg/kg)**

Ipilimumab **may not** be restarted while the patient is being treated with oral or intravenous corticosteroids for the management of immune related adverse events except for patients on stable doses of hormone replacement therapy for adrenal insufficiency such as hydrocortisone. In addition, patients must be off and have no requirement for oral/I.V. corticosteroids for at least 1 week and meet the other criteria for retreatment as outlined below.

Restart ipilimumab dosing if/when the adverse event(s) resolve(s) to  $\leq$  Grade 1

Rev. 2/14

severity or returns to baseline within 3 weeks of last dose administration:

- If the adverse event has resolved (to  $\leq$  Grade 1 severity or returns to baseline), restart ipilimumab dosing at the next scheduled time point per protocol.
- If the adverse event has not resolved in the protocol-specified dosing window (3 weeks [+/- 3 days], the next scheduled dose will be omitted.
- Patients with Grade 1 diarrhea and/or colitis who require steroid therapy must have resolution to grade 0 (baseline) before resuming dosing with ipilimumab. Patients with Grade  $\geq 2$  related diarrhea and/or colitis must have ipilimumab permanently discontinued (Section [5.5.1.1.3](#)).

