#### 5.5.1.1.3

#### **Criteria for permanent discontinuation of ipilimumab for Related Adverse Events on Arms A or D (ipilimumab 10mg/kg)**

Ipilimumab administration must be permanently discontinued for any of the following certainly, probably, or possibly treatment related adverse events, unless otherwise specified:

- Any  $\geq$  Grade 2 eye pain or reduction of visual acuity that does not respond to topical therapy and does not improve to  $\leq$  Grade 1 severity within 2 weeks of starting therapy, OR, requires systemic treatment.
- Any  $\geq$  Grade 2 diarrhea and/or colitis related to ipilimumab. Any  $\geq$  Grade 2 diarrhea/colitis should be considered RELATED unless immune related colitis is definitely ruled out (including by endoscopy and biopsy.)
- Any  $\geq$  Grade 2 hypophysitis, pneumonitis, nephritis, and/or sarcoid-like lesions.
- Any new motor or sensory neurologic toxicity  $\geq$  Grade 2 regardless of attribution (including Guillain-Barré syndrome and myasthenia gravis).
- Any  $\geq$  Grade 3 bronchospasm or other hypersensitivity reaction.

- Any other  $\geq$  Grade 3 non-skin adverse event with the exception of events listed under “Exceptions to Permanent Discontinuation” (Section [5.5.1.1.4](#)).
- AST or ALT  $>$  5 x ULN.
- Total Bilirubin  $>$  3 x ULN.
- Any other  $\geq$  Grade 4 laboratory abnormalities except for specified exceptions (Section 5.5.1.1.4).
- Any other  $\geq$  Grade 4 adverse event.
- Stevens-Johnson syndrome, toxic epidermal necrolysis, or rash complicated by full thickness dermal ulceration or necrotic, bullous, or hemorrhagic manifestations.
- Any adverse event, laboratory abnormality or intercurrent illness which, in the judgment of the investigator, presents a substantial clinical risk to the patient with continued dosing.
- Patients who require high dose steroids, other immune suppressants or anti-TNF drug therapy for the management of immune related adverse events as described in the Toxicity Management Guidelines/Algorithms should have ipilimumab permanently discontinued.

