#### 5.5.1.2.3

#### **Criteria for permanent discontinuation of ipilimumab for Related Adverse Events**

Ipilimumab administration must be permanently discontinued if any of the following Related Adverse Events occurs:

- Any  $\geq$  Grade 2 eye pain or reduction of visual acuity that does not respond to topical therapy and does not improve to  $\leq$  Grade 1 severity within 2 weeks of starting therapy, OR, requires systemic treatment.
- Any  $\geq$  Grade 2 hypophysitis.
- Any  $\geq$  Grade 3 bronchospasm or other hypersensitivity reaction.
- Any other  $\geq$  Grade 3 non-skin related adverse event with the exception of events listed under “Exceptions to Permanent Discontinuation” (Section [5.5.1.2.4](#)).
- Any  $\geq$  Grade 4 laboratory abnormalities, except for specified exceptions (Section [5.5.1.2.4](#)).
- For AST, ALT, or Total Bilirubin, then as follows:
  - AST or ALT  $> 5 \times$  ULN.
  - Total Bilirubin  $> 3 \times$  ULN.
- Any other  $\geq$  Grade 4 adverse event except for specified exceptions (Section [5.5.1.2.4](#)).
- Stevens-Johnson syndrome, toxic epidermal necrolysis, or rash

complicated by full thickness dermal ulceration or necrotic, bullous, or hemorrhagic manifestations.

- Any adverse event, laboratory abnormality or intercurrent illness which, in the judgment of the investigator, presents a substantial clinical risk to the patient with continued dosing.
- Any motor or sensory neurologic toxicity  $\geq$  Grade 3 regardless of attribution.
- Diagnosis with Guillain-Barré syndrome or myasthenia gravis (any grade).
- Patients who require high dose steroids, other immune suppressants or anti-TNF drug therapy for the management of immune related adverse events as described in the Toxicity Management Guidelines/Algorithms should have ipilimumab permanently discontinued. Treatment with oral budesonide or moderate dose steroids for grade 2 colitis or grade 2 or lower skin rash or higher dose IV steroids for grade 3 skin rash are criteria for ipilimumab dose delay but not permanent discontinuation.

Rev. 9/14

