For rising LFTs with AST/ALT > 5X ULN or total bilirubin >3X the ULN or suspected immune-mediated hepatitis:

Rev. 2/13

- a. Admit subject to hospital for evaluation and close monitoring.
- b. Stop any further ipilimumab dosing per protocol (Section [5.5.1.2.3](#) of protocol).

Rev. 2/13

- c. Start at least 2 mg/kg methylprednisolone sodium succinate per day, given IV as a single or divided dose.
- d. Check liver laboratory test values (LFTs, T-bilirubin) daily until stable or showing signs of improvement for at least 3 consecutive days.
- e. If no decrease in LFTs after 3 days or rebound hepatitis occurs despite treatment with corticosteroids, then add mycophenolate mofetil 1g BID per institutional guidelines for immunosuppression of liver transplants (supportive treatment as required, including prophylaxis for opportunistic infections per institutional guidelines).
- f. If no improvement after 5 to 7 days, consider adding 0.10 to 0.15 mg/kg/day of tacrolimus (trough level 5-20 ng/mL)
- g. If target trough level is achieved with tacrolimus but no improvement is observed after 5 to 7 days, consider other immunosuppressive therapy per institutional guidelines and in consultation with hepatology.
- h. Continue to check LFTs daily for at least 2 weeks to monitor sustained response to treatment.

Rev. 2/13

5.5.1.5.3 **Pancreas**

Symptoms of abdominal pain associated with elevations of amylase and lipase, suggestive of pancreatitis, may rarely be associated with anti-CTLA-4 monoclonal antibody administration. The differential diagnosis of acute abdominal pain should include pancreatitis. Appropriate workup should include serum amylase and lipase tests.

5.5.1.5.4 **Skin**

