**E1609 (Arms A and D & C and F) Hepatotoxicity Management Algorithm**

Rev. 2/13, 11/13,  
9/14

\*Ipilimumab may be held/delayed rather than discontinued if AST/ALT  $\leq 5 \times$  ULN and Tbili  $\leq 3 \times$  ULN. Resume ipilimumab when AST/ALT/Tbili return to grade 1 and meet protocol specific retreatment criteria.

\*\*The recommended starting dose for grade 4 hepatitis is 2 mg/kg/day methylprednisolone IV.

[figure not shown]
Patients on IV steroids may be switched to oral corticosteroid (e.g., prednisone) at an equivalent dose at start of tapering or earlier, once sustained clinical improvement is observed. Lower bioavailability of oral corticosteroids should be taken into account when switching to the equivalent dose of PO corticosteroids. Ipilimumab may not be restarted while the patient is being treated with systemic corticosteroids except for patients on stable doses of hormone replacement therapy such as hydrocortisone.

**A Phase III Randomized Study of Adjuvant Ipilimumab Anti-CTLA4 Therapy Versus High Dose Interferon a-2b for Resected High risk Melanoma**

**Appendix XVI  
Endocrinopathy Management Algorithm**

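### Ipilimumab hold-or-stop rules are undetermined for suspected immune hepatitis at lower liver-test values and for treatment-related Grade 3 laboratory abnormalities

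*Combined protocol and SAP*

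**What the plan says.** Ipilimumab has no dose reductions. Sections 5.5.1.1 (Arms A and D) and 5.5.1.2 (Arms C and F) each give a delay list, a resume rule, a permanent-stop list and exceptions to stopping. The investigator is told to check the delay list first, and then whether the stop list applies too.

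**Laboratory values**

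- *Delay (5.5.1.1.1, 5.5.1.2.1).* The general line, from Grade 2, covers a "non-skin related adverse event (including IRAEs) except for laboratory abnormalities". Laboratory values have two lines of their own. One, from Grade 2, covers values secondary to an immune event, with neutropenia, amylase, lipase, CPK and elevated liver tests as examples. The other covers any other value at or above a "Grade 3 laboratory abnormality".
- *Resume (5.5.1.1.2, 5.5.1.2.2).* Once the event is back to Grade 1 or baseline: "restart ipilimumab dosing at the next scheduled time point per protocol".
- *Stop (5.5.1.1.3).* At or above the stated grade, any other "Grade 3 non-skin adverse event with the exception of events listed under" the exceptions section. Separate lines cover AST/ALT above 5x ULN, total bilirubin above 3x ULN, and, at or above the stated grade, "Grade 4 laboratory abnormalities except for specified exceptions". Section 5.5.1.2.3 has the same structure: "Grade 3 non-skin related adverse event with the exception of events listed under" its own exceptions, plus a Grade 4 laboratory line.
- *Exceptions (5.5.1.1.4, 5.5.1.2.4).* The laboratory exception applies only to values unrelated to study treatment.

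**Liver**

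- *Section 5.5.1.5.2.* A lettered list applies to rising liver tests with AST/ALT above 5x ULN or bilirubin above 3x ULN, or to suspected immune-mediated hepatitis. Item b reads "Stop any further ipilimumab dosing per protocol" and cites only Section 5.5.1.2.3. Item c starts methylprednisolone at 2 mg/kg per day or more.
- *Appendix XV, all ipilimumab arms.* "Ipilimumab may be held/delayed rather than discontinued if AST/ALT" is at or below 5x ULN and total bilirubin is at or below 3x ULN, with resumption at Grade 1 if the retreatment criteria are met.

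**The concern.** With no dose reductions, hold or stop is the main dosing decision once a toxicity occurs. A patient whose event supports both readings could be stopped for good by one investigator and re-dosed by another, each following the text. Delivered dose, discontinuation rates and later toxicity would then depend partly on how the protocol was read. Safety and tolerability at each dose is a secondary endpoint (Section 2.2.1), and Section 5.5 records that the 10 mg/kg rules were tightened because severe toxicity was more frequent there. The rules that separate holding from stopping should therefore give one answer per event.

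**Working it through.** No sample size, event count or error rate is involved. The check follows two events through the lists.

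**Event 1: suspected immune-mediated hepatitis, AST/ALT at or below 5x ULN and bilirubin at or below 3x ULN.**

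1. Section 5.5.1.5.2: the patient enters the lettered list, because suspicion of immune hepatitis is an alternative trigger with no threshold. Item b says stop.
2. Item b could be conditional, since it defers to a section whose liver-test thresholds are above 5x and above 3x ULN. Item c then matters. The same section gives 1-2 mg/kg once or twice daily as its example of high-dose steroid, and item c's 2 mg/kg per day lies in that range. Both stop lists permanently stop patients who need high-dose steroids for an immune-related event. The list therefore still leads to a stop.
3. Delay lists: elevated liver tests of Grade 2 or higher that are secondary to an immune event are a delay event, with resumption available.
4. Appendix XV footnote: hold and resume is allowed in exactly this range, with no exception stated for suspected immune hepatitis.

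Steps 1-2 give stop; steps 3-4 give hold and resume.

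**Event 2: treatment-related Grade 3 laboratory abnormality other than AST/ALT or bilirubin.**

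| Reading | Delay list | Stop list | Outcome | Difficulty |
|---|---|---|---|---|
| Literal | Applies | Grade 3 non-skin line applies; the exception needs an unrelated value | Permanent stop | For related values, the Grade 4 laboratory line and the AST/ALT line add nothing (Section 5.5.2.8 labels more than 5 times normal as Grade 3 or 4) |
| Laboratory lines govern | Applies | Only the Grade 4 laboratory line is relevant; not met | Delay and resume | Needs an exclusion that the stop line lacks, although the parallel delay line has it |

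One reading makes other lines redundant; the other supplies missing words. The result is the same for Arms A/D and C/F.

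**Scale.** Planned doses are 4 induction + 4 maintenance = 8, so a stop after dose 1 forgoes up to 8 - 1 = 7. The documents give no rate for either event in this trial. The nearest figures are in Section 1.5.4.3, for earlier 10 mg/kg studies: inflammatory hepatotoxicity of any grade in 59/658 and Grade 3-4 in 42/658. The difference is 59 - 42 = 17, and 17/658 = 2.6%. That only indicates how common lower-grade hepatotoxicity was in another population. It counts neither suspected immune hepatitis nor patients handled inconsistently.

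**The case against.** **Laboratory values.** A reader might infer that an event on both the delay and the stop list is a flat contradiction. It is not: the two-step review expects some events to be on both. The stop lists also carry their own laboratory lines, and the Grade 4 line would be pointless for related values if the Grade 3 non-skin line already covered them. That is a fair argument for delay only, and it stands as the more coherent reading of the stop list alone. It does not settle the matter, because the drafters excluded laboratory values in the delay line and not in the stop line, and limited the laboratory exception to unrelated values.

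**Liver.** Section 5.5.1.5.2 also says that for rising liver tests dosing is held under the delay and discontinuation guidelines, and Section 5.5.1.5 describes this material as suggested, though strongly recommended. Item b, that sentence and the footnote all defer to Section 5.5.1. So item b can be read as conditional, but the steroid step still leads to a stop. The Appendix XV flow chart is not visible in the text available here, so the box that the footnote qualifies should be checked. The delay bullets do not depend on that figure. The cross-reference to the Arms C/F list alone changes no liver threshold, since both stop lists use the same ones. It is still wrong for text that serves all ipilimumab arms.

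**Consequence.** A reader might also infer a count of affected patients per arm, or that sites did diverge and the results are distorted. The documents support neither: they give no rate and no evidence of divergent handling. New wording cannot reach adult dosing. Adult accrual closed on August 15, 2014, therapy lasts about 60 weeks, and the final analysis is set for February 2019. Adolescent ipilimumab arms are capped at 15 each.

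**Conclusion.** Two inconsistencies stand. The hepatitis one is the clearer: stop in Section 5.5.1.5.2, hold and resume in Appendix XV and the delay lists, for the same patient when AST/ALT is at or below 5x ULN and bilirubin at or below 3x ULN. The laboratory one is an ambiguity with two defensible outcomes, in both dose groups, for treatment-related Grade 3 values other than AST/ALT or bilirubin.

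The number of patients affected cannot be derived from the documents. Alpha, power and the intent-to-treat comparison as defined are untouched. What is exposed is the interpretation of discontinuation, dose delivered and toxicity by arm. The hepatitis conclusion assumes that the Appendix XV flow chart does not itself exempt suspected immune hepatitis from the footnote.

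**What to change.** - Reconcile item b of the lettered list in Section 5.5.1.5.2 with the Appendix XV footnote and with the elevated-liver-test delay bullets in 5.5.1.1.1 and 5.5.1.2.1. Cite 5.5.1.1.3 for Arms A/D and 5.5.1.2.3 for Arms C/F.
- In the Grade 3 non-skin bullets of 5.5.1.1.3 and 5.5.1.2.3, state whether laboratory values are included, so that each event falls under one rule.
- Document which reading was applied to patients already treated, so that discontinuations by arm can be interpreted.

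Which rule or threshold applies is for the clinical team. The first two items cost a few lines of protocol wording. The third needs a look back through the treatment and toxicity forms, with no change to the design or the primary analysis.

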#### 5.5.1.1.4

#### **Exceptions to permanent discontinuation of ipilimumab on Arms A and D (ipilimumab 10mg/kg)**

Ipilimumab administration may be resumed in the following cases:

- Potentially reversible inflammation ( $<$  Grade 4), attributable to a local anti-tumor reaction and a potential therapeutic response. This includes inflammatory reactions at sites of tumor resections or in draining lymph nodes, or at sites suspicious for, but not diagnostic of metastasis.
- Laboratory abnormalities that are rapidly reversible, not life threatening, do not reflect underlying organ system dysfunction, and are not related to the study treatment, such as transient elevations of uric acid, hypocalcaemia, hypophosphatemia.

- Hospitalization for  $\leq$  Grade 2 adverse events (not including Grade 2 events that require permanent discontinuation as listed under Section [5.5.1.1.3](#)) where the primary reason for hospitalization is to expedite the clinical work-up.
- Patients with the following conditions where in the investigator's opinion continuing study drug administration is justified:
  - Ocular toxicity that has responded to topical therapy and has improved to  $\leq$  Grade 1 severity within 2 weeks of starting therapy.
  - Patients without a diagnosis of hypophysitis who have Grade 2 hypothyroidism, Grade 2 low testosterone or Grade 2 adrenal insufficiency where clinical symptoms are controlled with appropriate hormone replacement therapy.

Rev. 11/13,  
9/14

#### 5.5.1.2 Dose and Schedule Modifications for **Arms C and F (Ipilimumab 3 mg/kg)**

There will be no dose reductions for ipilimumab. The dose of ipilimumab will either be given or delayed/discontinued. Patients may develop study drug-related toxicities that may require skipping doses or dose discontinuation. Some of these adverse events may be consistent with potentially drug-related immune-mediated phenomena; termed IRAEs ([Appendix XIII-Appendix XVII](#)). Details of how to dose study medication in the presence of adverse drug reactions that may or may not be IRAEs are addressed below.

Patients will delay or discontinue treatment with ipilimumab if they experience at least one adverse event, specified below, considered by the investigator to be **certainly, probably, or possibly** related to ipilimumab treatment unless otherwise specified. The following criteria will be used to determine dosing delay, restarting doses, or discontinuing ipilimumab. For an adverse event, review the following criteria in a stepwise manner: First, assess the dose delay criteria and decide whether a scheduled dose should be delayed. Second, determine whether the permanent discontinuation criteria apply to the adverse event in question as well.

**NOTE:** Due to the possible effect of treatment with ipilimumab on the immunologic response to infectious disease vaccines, patients must not

Rev. 8/12

have had any infectious disease vaccination (e.g., standard influenza, H1N1 influenza, pneumococcal, meningococcal, tetanus toxoid) 4 weeks before or after any dose of ipilimumab.

Rev. 9/14

5.5.1.2.1 **Criteria to delay/skip one dose of ipilimumab on Arms C and F (ipilimumab 3 mg/kg)**

Delay ipilimumab dosing for the following certainly, probably, or possibly treatment related adverse events, unless otherwise specified:

- Any  $\geq$  Grade 2 non-skin related adverse event (including IRAEs) except for laboratory abnormalities.
- Grade  $\geq$  2 laboratory abnormalities that are secondary to an immune-related adverse event or autoimmune phenomenon (e.g., Grade  $\geq$  2 TSH associated with a CTCAE v.4 grade 2 thyroid dysfunction induced by ipilimumab, anemia, neutropenia, amylase, lipase, CPK, hyperglycemia, or elevated LFTs) should also lead to an ipilimumab dosing delay/skipping.
- Any other  $\geq$  Grade 3 laboratory abnormality.
- Any  $\geq$  Grade 3 skin-related adverse event (including IRAEs) regardless of attribution.

Rev. 2/12,  
9/14

5.5.1.2.2 **Criteria to resume ipilimumab treatment on Arms C and F (ipilimumab 3mg/kg)**

Ipilimumab may not be restarted while the patient is being treated with oral or intravenous corticosteroids for the management of immune related adverse events except for patients on stable doses of hormone replacement therapy for adrenal insufficiency such as hydrocortisone. In addition, patients must be off and have no requirement for oral/I.V. corticosteroids for at least 1 week and meet the other criteria for retreatment as outlined below.

Restart ipilimumab dosing if/when the adverse event(s) resolve(s) to  $\leq$  Grade 1 severity or returns to baseline within 3 weeks of initial dose administration:

- If the adverse event has resolved (to  $\leq$  Grade 1 severity or returns to baseline), restart ipilimumab dosing at the next scheduled time point per protocol.
- If the adverse event has not resolved in the protocol-specified dosing window (3 weeks  $[\pm 3 \text{ days}]$ ), the next scheduled dose will be omitted.
- Patients with Grade 2 diarrhea/colitis must have resolution to Grade 0 (baseline) severity and must have a follow-up colonoscopy to document endoscopic (with or without pathologic) resolution of inflammation before resuming dosing with ipilimumab.

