#### **Induction Phase**

Ipilimumab 10 mg/kg (Arms A, D) or 3 mg/kg (Arms C, F), administered by IV infusion every 3 weeks for a total of four doses.

Rev. 2/12

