#### **Maintenance Phase**

Ipilimumab 10 mg/kg (Arms A, D) or 3 mg/kg (Arms C, F), administered by IV infusion every 12 weeks (3 months), beginning at week 24, then at weeks 36, 48, and 60.

Rev. 2/12

Dose delays are allowed as per the dosing criteria described later in this section. Infusions should be given over 90 minutes (not bolus or IV push).

5.2.1.4 Dose Calculations: Calculate **Total Dose** as follows:

Rev. 2/12

Patient body weight in kg x [10 mg or 3 mg/kg] = total dose in mg

Calculate **Total Infusion Volume** as follows:

Total dose in mg ÷ 5 mg/mL = infusion volume in mL

Calculate **Rate of Infusion** as follows:

Infusion volume in mL ÷ 90 minutes = rate of infusion in mL/min.

Rev. 2/12

For example, a patient on Arms A or D (10 mg/kg) weighing 114 kg (250 lb) would be administered 1140 mg of ipilimumab (114 kg x 10 mg/kg = 1140 mg) with an infusion volume of 228 mL (1140 mg ÷ 5 mg/mL = 228 mL) at a rate of approximately 2.5 mL/min (228 mL ÷ 90 minutes) in 90 minutes.

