**E1609 (Arms C and F) GI Management Algorithm**

\*\* Patients with Grade 2 colitis who require steroid therapy with resolution to ≤ Grade 1 severity must have a follow-up colonoscopy to document endoscopic (with or without pathologic) resolution of inflammation before resuming dosing with ipilimumab.

[figure not shown]
Patients on IV steroids may be switched to oral corticosteroid (e.g., prednisone) at an equivalent dose at start of tapering or earlier, once sustained clinical improvement is observed. Lower bioavailability of oral corticosteroids should be taken into account when switching to the equivalent dose of PO corticosteroids. Ipilimumab may not be restarted while the patient is being treated with systemic corticosteroids except for patients on stable doses of hormone replacement therapy such as hydrocortisone.

**A Phase III Randomized Study of Adjuvant Ipilimumab Anti-CTLA4 Therapy Versus High Dose Interferon a-2b for Resected High risk Melanoma**

**Appendix XV  
Hepatotoxicity Management Algorithms**

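### Arms C and F: Section 5.5.1.2.2 and the Appendix XIV footnote attach different conditions to resuming ipilimumab after Grade 2 diarrhea/colitis, and nothing says expressly which governs

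*Combined protocol and SAP*

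**What the plan says.** **Main text, Arms C and F.** Section 5.5.1.2.2 gives a general restart condition (Grade 1 or less, or back to baseline) and then a specific one: "Patients with Grade 2 diarrhea/colitis must have resolution to Grade 0 (baseline) severity and must have a follow-up colonoscopy". The colonoscopy has to show endoscopically that inflammation has cleared before dosing resumes. The bullet names diarrhea as well as colitis and does not mention steroid treatment.

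**Appendix XIV, Arms C and F.** The footnote to the GI algorithm says "Patients with Grade 2 colitis who require steroid therapy with resolution to ≤ Grade 1 severity must have a follow-up colonoscopy", again showing resolution of inflammation before dosing resumes. It names colitis only, and only cases that needed steroids.

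**Who may resume.** Section 5.5.1.2.3 says that oral budesonide or moderate-dose steroids for Grade 2 colitis "are criteria for ipilimumab dose delay but not permanent discontinuation". The patients in the footnote are therefore candidates for re-treatment.

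**The 3-week window.** The lead-in sentence of 5.5.1.2.2 (Arms C and F) reads "severity or returns to baseline within 3 weeks of initial dose administration". The parallel sentence of 5.5.1.1.2 (Arms A and D) reads "severity or returns to baseline within 3 weeks of last dose administration".

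**The concern.** Two pages of one protocol give binding-sounding instructions for the same decision on the same arms, and they differ in recovery grade, in the event covered and in who needs a colonoscopy. Sites are directed to both. Section 5.5.1.2 presents its criteria as the ones for delaying, restarting and stopping the drug. Appendix XIV tells sites, in capitals, to use the algorithm for the patient's arm.

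Colitis and diarrhea are among the main severe toxicities of ipilimumab. If sites work from different pages, the same patient could be re-treated at different states of recovery, and a given restart could be called compliant on one page and a deviation on the other. Arm C is the experimental arm of the first-step comparison and Arm F is an adolescent arm whose primary objective is safety, so a consistent record of restarts has value.

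**Working it through.** No figure in the plan can be reproduced here. The check is a comparison of texts, followed by a bound on the number of patients.

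**1. Resumption conditions, Arms C and F**

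| Element | Section 5.5.1.2.2 | Appendix XIV footnote |
|---|---|---|
| Event | Grade 2 diarrhea or colitis | Grade 2 colitis |
| Steroid condition | None | Only if steroids were needed |
| Grade named | 0 (baseline) | 1 or less |
| Colonoscopy | All cases | Cases meeting the two conditions above |

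**2. The two texts applied to four patients.** Each is assumed to meet every other restart condition, including at least one week off oral or IV steroids.

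- Steroid-treated Grade 2 colitis, now Grade 0, clear colonoscopy: both texts are satisfied.
- Steroid-treated Grade 2 colitis, now Grade 1, clear colonoscopy: the section bars resumption; the footnote can be read as allowing it.
- Grade 2 colitis without steroids, now Grade 0, no colonoscopy: the section bars resumption; the footnote asks for no colonoscopy.
- Grade 2 diarrhea without a diagnosis of colitis, now Grade 0, no colonoscopy: the section bars resumption; the footnote does not cover the case.

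The texts can diverge for the last three. These are foreseeable patients: Section 5.5.1.5.1 expects some Grade 2 cases to be managed conservatively and others to move to steroids.

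**3. The 3-week window.** Induction is "administered by IV infusion every 3 weeks for a total of four doses", and the calendar in Section 7.2 puts those doses at Days 1, 22, 43 and 64. Maintenance follows, "beginning at week 24, then at weeks 36, 48, and 60".

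- Counted from the initial dose: Day 1 + 21 days = Day 22, the day on which dose 2 is due. Taken alone, the C/F lead-in cannot be met for an event that starts after dose 2 or later.
- Counted from the last dose: after dose 2 the window runs to Day 22 + 21 days = Day 43, and it moves forward with each dose.

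The bullets below both lead-ins agree. A resolved event means restarting at the next scheduled time point. An event not resolved within 3 weeks (±3 days) means omitting the next scheduled dose.

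**4. How many patients.** The plan gives no count of Grade 2 cases. Section 9.7.1 quotes immune-related diarrhea of any grade in 27 to 31% of patients in the ipilimumab groups of the earlier phase III trial at 3 mg/kg. Applied to about 500 adults on Arm C:

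- 0.27 × 500 = 135
- 0.31 × 500 = 155

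These counts include Grade 1, which does not trigger the C/F delay rule (5.5.1.2.1), and Grade 3 or higher, which leads to permanent discontinuation subject to listed exceptions (5.5.1.2.3). Only the Grade 2 share is in scope, and within it only patients on whom the texts diverge. Arm F adds at most 15 patients in all. Carrying the rate over from metastatic disease to the adjuvant setting is an assumption.

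**The case against.** The strongest reply is that the two GI texts are compatible. The footnote does not say that dosing may resume at Grade 1; it says which patients must have a colonoscopy first. A site that follows Section 5.5.1.2.2 to the letter breaches nothing in the footnote. A reader might infer that Appendix XIV sets a competing resumption threshold of Grade 1. The documents do not support that: Grade 1 or less is attached to the colonoscopy, and the flow chart to which the footnote belongs is not shown, so any grade printed there cannot be checked.

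The documents also lean toward the section. Section 5.5.1.2 introduces its criteria as those to be used for restarting doses, while Section 5.5.1.5 calls the algorithms suggested, though strongly recommended. This stands as an indication, but it is not a precedence clause. It also leaves in place an appendix that sites are told to use and that is narrower on event and colonoscopy.

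On the window, a reader might infer that a C/F patient with an event after dose 2 could never restart. That holds only for the lead-in read without its own bullets. With them, the stated consequence of an unresolved event is an omitted dose, and the practical effect of the wording is small. Whether the difference between arms was intended is not stated.

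On timing, adult accrual to Arms A, B and C closed on August 15, 2014 and ipilimumab lasts about 60 weeks, so scheduled adult dosing would have ended around October 2015. Adolescent enrolment was to stay open only until 2016. This objection is sound: rewording now changes little future dosing. It would still settle how past restarts are classified and cover any remaining dosing, including re-starts after operable recurrence under Section 5.2.3.

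**Conclusion.** The inconsistency is real and limited. For Arms C and F, the main text and the appendix footnote differ on the grade named, the event covered and who needs a colonoscopy before resumption, and no sentence says expressly which governs. The difference in reference dose for the 3-week window is a secondary drafting point.

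The size cannot be stated. The range of 135 to 155 patients is an upper bound, on the assumption that the quoted rate carries over to Arm C. A reader might take 27 to 31% as the share of the arm affected; the documents do not support that, because the figure covers all grades and the Grade 2 share is not given. Nor do they show an effect on dose exposure or on the primary comparison. Sample size, alpha and power do not depend on this rule.

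The conclusion rests on the footnote text alone, since the flow chart is not shown. It takes no view on which clinical rule is right.

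**What to change.** Reconcile Section 5.5.1.2.2 and the Appendix XIV footnote for Arms C and F so that both give the same resumption grade, the same event definition (diarrhea, colitis or both) and the same colonoscopy requirement, including whether it depends on steroid use. Check the flow chart against the result, and add a sentence saying whether the section or the algorithm governs if they differ.

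Reconcile the dose from which the 3-week window is counted in Sections 5.5.1.1.2 and 5.5.1.2.2, or state that the difference between the arm groups is intended.

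The clinical content of each rule is for the study's clinical leadership to decide. The cost is protocol wording only; the statistical design and the data already collected are unaffected. If restarts on Arms C and F have been reviewed for compliance, record which text was used as the standard.
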